2.3 Primary Endpoints

- 2.3.1** The overall FLT-PET bone marrow signal will be defined as the average maximum FLT SUV within the vertebrae, pelvis, and bilateral femurs measured at the time of early engraftment. This scan will be obtained on transplant day +25 +/- 5 days. Complete donor reconstitution will be defined as chimerisms $\geq 95\%$ within the CD3 and unfractionated compartments on bone marrow biopsy/aspirate obtained on transplant day +35
- 2.3.2** The overall FLT-PET signal within host secondary lymphoid tissue will be defined as the average maximum FLT SUV within the spleen, cervical lymph nodes, axillary lymph nodes, inguinal lymph nodes, and mesenteric lymph nodes. This scan will be obtained on transplant day +60 +/- 5 days. Acute GVHD will be diagnosed either clinically or preferably pathologically within any target organ by transplant day +100.

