1.0 BACKGROUND AND RATIONALE

1.1 Study Synopsis

This is a non-randomized, prospective pilot study exploring the use of fluorothymidine (FLT)-PET-MRI in the evaluation of allogeneic bone marrow transplant patients to potentially predict engraftment success, malignancy relapse, and the development of graft versus host. A total of 12 patients who have undergone allogeneic bone marrow transplantation will undergo FLT-PET-MRI imaging on two separate occasions. The first scan will occur immediately after initial neutrophil count recovery on day +25. The second scan will occur on transplant day +60 by which time stable count recovery should have occurred. The findings on the first scan will be correlated with clinical outcomes and pathological results on transplant day +35, and the findings on the second scan will be correlated with clinical outcomes and pathological results on day +100. The day +35 and +100 time points were chosen because allogeneic transplant patients at our institution undergo a restaging bone marrow biopsy and aspirate with donor/recipient chimerism studies around these days as part of our usual standard of care. In addition to the 12 allogeneic transplant patients, 3 patients undergoing autologous stem cell transplant will also be imaged at the same two time points in order to determine how much of the FLT signal observed after allogeneic transplant is unique to that population and the result of allo-antigen driven T cell expansion.

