The current proposal explores the use of a novel imaging modality, FLT PET/MRI, to correlate allogeneic transplant outcomes with FLT and MRI findings during early stem cell engraftment and at a later time point following stable count recovery. Specifically, we will determine if the strength of the early FLT signal within the bone marrow correlates with engraftment success and if isolated areas of cellular proliferation within the marrow at a later time point might predict for leukemia relapse. In addition, based on the important role that host lymphoid tissues are known to play in GVHD pathogenesis in mice, we will determine if the FLT signal within host SLT after transplant can predict for the development of GVHD in human BMT patients. Because FLT imaging by itself cannot distinguish between bone marrow engraftment/proliferation and the allo-immune driven T cell expansion that ultimately results in GVHD, we will image autologous transplant patients as a comparator arm. Autologous HSCT like allogeneic transplantation involves the administration of very high doses of chemotherapy to high risk cancer patients in order to achieve better tumor kill. However, in this situation patients are administered their own cryopreserved stem cells to reconstitute the ablated hematopoietic system. Under those circumstances there is no allo-immune reactivity to drive T cell activation and expansion after transplant, and as a result there is no GVHD in the autologous transplant setting. Thus, these patients will help us to

elucidate how much of the FLT signal seen in the allogeneic setting is the result of allo-immune driven T cell expansion.

FLT-Imaging: Fluorodeoxyglucose (FDG)-PET detects the accumulation of FDG in glucose-avid tissue, and is a measure of overall metabolic activity. FDG is relatively simple to synthesize, has a long half-life (approximately 2 hours), and has a well-understood mechanism of uptake, making it the most commonly used radiotracer in oncology.^{5,6}

The diagnostic value of FDG-PET, however, is limited by its lack of specificity. There has been great interest in taking advantage of the various unique properties of tumor cells in PET imaging. Tumor and expanding inflammatory cells show increased DNA synthesis during cellular proliferation, making the DNA synthetic pathway an attractive target for their visualization.

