2.0 STUDY OBJECTIVES AND ENDPOINTS

Primary Objectives

- 2.1.1** To compare the overall FLT-PET bone marrow signal on transplant day +25 between allogeneic stem cell transplant recipients who do and do not go on to achieve complete donor bone marrow reconstitution by transplant day +35.
- 2.1.2** To compare the overall FLT-PET signal intensity within host secondary lymphoid sites on transplant day +60 between allogeneic stem cell transplant recipients who do and do not develop acute GVHD by transplant day +100.

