4.5 Medical Records Abstraction

Objectives of this study include identifying quantitative imaging markers that best predict engraftment quality and GVHD development in allogeneic HSCT patients. To achieve this aim, we will correlate the imaging data with the need for blood product transfusion support, biopsy based measures of bone marrow donor/recipient chimerism studies and overall bone marrow cellularity, and the clinical and/or histopathological documentation of graft versus host disease.

Patient pathology records will be obtained after the 100-day follow-up period has passed and again one year post-transplant or at the time of death if the patient expires prior to then

All patients receiving HSCT have outcomes data collected for quality and program performance assessments. This data is collected for every patient until either death or lost to follow-up. The data routinely collected includes demographic data, donor match information, and outcomes of engraftment, survival, disease relapse, and development of acute and chronic GVHD.

Image Analysis

Quantitative T1 and DWI ADC maps will be computed. Regions of interests (ROIs) will be drawn on the anatomic MR images (blinded to SUV values and clinical outcome), then transferred to FLT SUV maps. We will correlate the imaging data with the histopathological data to identify the quantitative markers that best predict engraftment quality.

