8.0 STATISTICAL CONSIDERATIONS

8.1 Study Design

This is a non-randomized, prospective pilot study exploring the use of FLT-PET-MRI in the evaluation of allogeneic patients after bone marrow transplants to potentially predict engraftment success and the development of graft versus host disease. A total of 15 patients who have undergone bone marrow transplantation will receive FLT-PET-MRI imaging, 3 autologous and 12 allogenic recipients will be recruited. The 3 autologous patients are included as a comparator arm to help elucidate how much of the FLT signal in allogeneic HSCT patients is related to allo-antigen driven T cell proliferation and therefore unique to the allogeneic setting.

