8.3 Data Analysis Plans

8.3.1 Primary Analysis

Experimental measurements will be obtained at two time points: around day +21 (at the time of initial neutrophil engraftment) and around day +60 (after stable count recovery). FLT standardized uptake value (SUV) will be evaluated within the following target organs: The marrow signal will be evaluated in the pelvis, vertebrae, and bilateral femurs. The secondary lymphoid tissue signal will be evaluated in the spleen, inguinal lymph nodes, axillary lymph nodes, cervical lymph nodes, and mesenteric lymph nodes). We will plan to image 3 autograft and 12 allograft patients.

Wilcoxon Rank sum tests will be used to compare signals between the groups. Spearman and Pearson correlation coefficients will be used to measure correlations between pairs of continuous variables. ROC analyses will be performed to explore the sensitivity/specificity of signal ratio cutoffs for the outcomes of Complete Donor Reconstitution and GVHD.

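### The day +60 lymphoid FLT comparison does not separate acute GVHD that began before the scan from GVHD that began after it, so by itself it cannot support the predictive aim

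*Combined protocol and SAP*

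**What the plan says.** Objective 2.1.2 is "To compare the overall FLT-PET signal intensity within host secondary lymphoid sites on transplant day +60" between allogeneic recipients who do and do not develop acute GVHD by day +100. Endpoint 2.3.2 places the scan at day +60 +/- 5 and defines the outcome: "Acute GVHD will be diagnosed either clinically or preferably pathologically within any target organ by transplant day +100". Secondary endpoint 2.4.2 uses the same outcome with the day +25 scan.

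Section 8.3.1 gives the analysis: "Wilcoxon Rank sum tests will be used to compare signals between the groups", and "ROC analyses will be performed to explore the sensitivity/specificity of signal ratio cutoffs for the outcomes of Complete Donor Reconstitution and GVHD". Section 8.2 expects acute GVHD in roughly 30-40% of patients by day +100, any site and grade.

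The purpose is stated as prediction in several places:
- Synopsis (1.1): "to potentially predict engraftment success, malignancy relapse, and the development of graft versus host"
- Rationale (1.1.1): "we will determine if the FLT signal within host SLT after transplant can predict for the development of GVHD in human BMT patients"
- Section 4.5: "identifying quantitative imaging markers that best predict engraftment quality and GVHD development in allogeneic HSCT patients"
- Section 8.1: "to potentially predict engraftment success and the development of graft versus host disease"

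No section sets a start to the GVHD window, requires freedom from GVHD at the scan, or divides cases by onset relative to the scan. The eligibility criteria do not exclude earlier acute GVHD. Section 3.2.9 restricts scanning to outpatients, which may keep some active cases off the scanner but not outpatient or already treated ones.

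**The concern.** Section 1.1.1 says acute GVHD usually appears in the first few months after transplant, so onsets before day +60 are to be expected. It also says GVHD is treated by increasing immunosuppression, so an earlier case may already be under treatment when scanned. The hypothesis is that donor T cells expand in lymphoid tissue before they damage target organs, which makes the order of scan and onset central.

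With the groups pooled, a positive result could mean only that existing GVHD raises the lymphoid signal. A null result could mean only that treated cases look normal. Neither can be told apart from the presence or absence of prediction. The pooled difference and ROC cutoffs would then go forward as planning values for the larger study named in 8.2.

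**Working it through.** **Inputs from the plan (8.2).** 12 allogeneic patients; 30-40% acute GVHD by day +100; rank-sum test, one-sided 0.10; target P = 0.854 that a non-GVHD value lies below a GVHD value.

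**Reproducing the plan's figure.** Noether's formula is power = Φ(√(12·N·c(1−c)) × (P − 0.5) − z₀.₉₀), with c the share of patients in one group. For 6 vs 6: √(12 × 12 × 0.25) = 6, and 6 × 0.354 − 1.2816 = 0.842, so Φ = 0.800. The stated 80% reproduces.

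**Expected cases.** 12 × 0.30 to 12 × 0.40 = 3.6 to 4.8. I use 4 vs 8.

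**Assumptions.** The documents give neither the share of onsets before the scan nor the effect of existing or treated GVHD on the signal. I assume two of the four onsets precede the scan, and unit-variance normal signals. P = 0.854 is then a shift of √2 × z(0.854) = 1.490 SD. The test is the exact one-sided rank-sum test, evaluated by simulation. At 4 vs 8 it rejects for U ≥ 25, with size 38/495 = 0.0768.

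**No predictive value, earlier cases raised.** Pooled AUC = (2 × 0.50 + 2 × AUC of earlier cases)/4.

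| Shift of the two earlier cases | Pooled AUC | Trials positive |
|---|---|---|
| +0.5 SD | 0.57 | 14% |
| +1.0 SD | 0.63 | 22% |
| +1.5 SD | 0.68 | 29% |

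**True prediction (later cases at P = 0.854).**

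| Shift of the two earlier cases | Pooled power |
|---|---|
| −1 SD | 5% |
| 0 | 29% |
| +0.5 SD | 48% |
| +1.0 SD | 65% |
| +1.5 SD | 79% |

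Onset after the scan only, 2 vs 8 (U ≥ 14, size 4/45 = 0.089), has 63% power. The split therefore gains power only when earlier cases look normal or low. Its benefit is interpretation.

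**Two opposite truths with the same pooled data.** Truth A: no prediction, earlier cases raised 1.49 SD. Truth B: full prediction, earlier cases at normal level. In both, the four GVHD shifts are {1.49, 1.49, 0, 0}, so both give 29% positive and pooled AUC (2 × 0.854 + 2 × 0.50)/4 = 0.677. This is so by construction; it shows the logic and is not an estimate of size. The later-onset analysis separates them: 9% vs 63% positive, AUC 0.50 vs 0.854.

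**What the later-onset comparison can deliver at P = 0.854.**

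| Later cases vs non-cases | Noether | Exact, normal shift |
|---|---|---|
| 3 vs 8 | √(12 × 24/11) = 5.117; Φ(0.530) = 70% | 76% |
| 2 vs 8 | √(12 × 16/10) = 4.382; Φ(0.270) = 61% | 63% |
| 1 vs 8 | not meaningful | cannot reject: smallest p = 1/9 = 0.111 |

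**Chance of at most one later case.** Binomial(12, q), with q = GVHD rate × (1 − share before the scan); shares assumed; rates 40% then 30%.
- A quarter before the scan: q = 0.30 to 0.225, chance 9% to 21%.
- Half: q = 0.20 to 0.15, chance 27% to 44% (at 0.20: 0.8¹² + 12 × 0.2 × 0.8¹¹ = 0.0687 + 0.2062 = 0.275).
- Three-quarters: q = 0.10 to 0.075, chance 66% to 77%.

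**The case against.** **The objective says compare, not predict.** True, and the null in 8.2 is no difference. A reader might infer that the test is invalid or its error rate inflated. The documents do not support that: for the null as written the test holds its size, and the 14-29% above are correct detections of a real association. The difficulty arises only when that association is read as prediction.

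**The window is silent, not stated to begin at transplant.** This stands. The wording about who does and does not develop GVHD could be taken as new onset. But 2.3.2 adds no such limit, and the 30-40% in 8.2 is a cumulative rate to day +100, so pooling is the plain reading.

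**Detecting early GVHD is also of interest.** Section 1.1.1 hopes imaging could flag these processes in their earliest stages, so a signal from GVHD just under way is not wholly off-aim. That does not cover cases already treated, and the pooled result cannot show which kind of case produced the difference.

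**The day +25 scan covers it.** It does so in part: only onsets before about day +25 are mixed in. But it is secondary, carries the same undivided outcome, and does not repair the primary endpoint. Because it exists, one should not infer that the trial says nothing about prediction.

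**Onset can be listed case by case at reporting.** Probably so, from the records in 4.5. What is lost is prespecification, which matters with four or five cases and exploratory cutoffs.

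**The later group may be untestable.** Correct, and it must be said in advance.

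**Conclusion.** The point holds as a limit on interpretation. The primary GVHD comparison is a valid association between day +60 lymphoid signal and acute GVHD by day +100. Unless onset before and after the scan is separated, neither it nor the GVHD ROC cutoffs can carry a predictive claim.

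The gap in the text is certain; its numerical effect is not. Every percentage for earlier cases rests on an assumed share of onsets and assumed SD shifts, and the effect could be small if few onsets precede day +60. Nor should a reader infer that splitting the cases generally raises power. For a pilot meant to inform a larger study, this should be fixed but does not undermine the trial.

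**What to change.** 1. Abstract the acute GVHD onset date relative to each scan.
2. Keep the overall comparison and label it an association.
3. In 2.3.2, 2.4.2 and 8.3.1, prespecify a companion analysis of onset after the scan among patients GVHD-free at that scan, with GVHD present at or before the scan reported separately.
4. Base any predictive statement and any GVHD ROC cutoff on the companion analysis only.
5. State in advance that it is descriptive when later cases are few, for example one.
6. Name one method for any power quoted for the later-onset comparison, and use it throughout.

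Which comparison is formally primary is for the sponsor. An immunosuppression item is not needed unless an analysis uses it. The 6 vs 6 assumption against the expected 30-40% rate is a separate point.

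The cost is an IRB-approved amendment and one abstracted date per case, with no new scans or visits. The date should be recoverable from the GVHD documentation in 4.5 and the clinic visits two to three times weekly to day +100 (5.1.1.2.1). The price is a small later-onset group that may be too small to test.

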2.4 Secondary Endpoints

- 2.4.1** The overall FLT-PET bone marrow signal will be defined as the average maximum FLT SUV within the vertebrae, pelvis, and bilateral femurs measured on transplant day +60. Complete donor reconstitution will be defined as chimerisms $\geq 95\%$ within the CD3 and unfractionated compartments on bone marrow biopsy/aspirate obtained on transplant day +100
- 2.4.2** The overall FLT-PET signal within host secondary lymphoid tissue will be defined as the average maximum FLT SUV within the spleen, cervical lymph nodes, axillary lymph nodes, inguinal lymph nodes, and mesenteric lymph nodes

on transplant day +25. Acute GVHD incidence will be diagnosed either clinically or preferably pathologically within any target organ by transplant day +100.

- 2.4.3** The overall FLT-PET signal within recipient secondary lymphoid tissue (average maximum FLT SUV within the spleen, cervical lymph nodes, axillary lymph nodes, inguinal lymph nodes, and mesenteric lymph nodes) and the bone marrow (average maximum FLT SUV within the vertebrae, pelvis, bilateral femurs) in autologous transplant recipients will be compared to the corresponding overall FLT-PET signals from allogeneic transplant recipients on transplant days +25 and +60.
- 2.4.4** Transfusion independence will be defined as not having received a packed red blood cell (PRBC) or platelet transfusion within the 7 days preceding the day +35 or the day +100 time point
- 2.4.5** Bone marrow cellularity will be defined in a dichotomous manner as either hypocellular or normocellular/hypercellular based on the bone marrow pathology report from the day +35 and day +100 bone marrow biopsies.
- 2.4.6** The average FLT SUV in the vertebral column will be compared to the quantitative T1 and Diffusion Weighted Imaging (DWI) signals in the vertebral column by MRI. The average FLT SUV in the pelvis will be compared to the quantitative T1 and Diffusion Weighted Imaging (DWI) signals in the pelvis by MRI. The average FLT SUV in the bilateral femurs will be compared to the quantitative T1 and Diffusion Weighted Imaging (DWI) signals in the bilateral femurs by MRI.

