2.2 Secondary Objectives

- 2.2.1** To compare the overall FLT-PET bone marrow signal on transplant day +60 between allogeneic stem cell transplant recipients who do and do not achieve complete donor bone marrow reconstitution by transplant day +100.
- 2.2.2** To compare the overall FLT-PET signal intensity within host secondary lymphoid sites on transplant day +25 between allogeneic stem cell transplant recipients who do and do not develop acute GVHD by transplant day +100
- 2.2.3** To evaluate differences in FLT uptake within the bone marrow and secondary lymphoid tissues in patients undergoing autologous HSCT versus allogeneic HSCT
- 2.2.4** To correlate the strength of the FLT-PET signal within the bone marrow on transplant day +25 with the rate of transfusion independence on transplant day +35 in allogeneic stem cell transplant recipients
- 2.2.5** To correlate the strength of the FLT-PET signal within the bone marrow on transplant day +25 with bone marrow cellularity on transplant day +35 in allogeneic stem cell transplant recipients.
- 2.2.6** To correlate the strength of the FLT-PET signal within the bone marrow on transplant day +60 with the rate of transfusion independence on transplant day +100 in allogeneic stem cell transplant recipients

- 2.2.7** To correlate the strength of the FLT-PET signal within the bone marrow on transplant day +60 with bone marrow cellularity on transplant day +100 in allogeneic stem cell transplant recipients
- 2.2.8** To evaluate if isolated or asymmetric foci of increased FLT within the bone marrow or lymph nodes on transplant day +60 are associated with the incidence of disease relapse by day +100 in allogeneic stem cell transplant recipients
- 2.2.9** To correlate the strength of the FLT-PET signal within the bone marrow on transplant day +25 and on day +60 with MRI findings suggestive of engraftment in allogeneic stem cell transplant recipients
- 2.2.10** To evaluate the association of the overall FLT-PET signal intensity within host secondary lymphoid sites on transplant day +60 with the overall incidence of acute graft versus host disease and malignancy relapse over the first transplant year

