8.2 Sample Size and Accrual

This is a pilot study to gather preliminary data, and the results from this study will be used to power a future larger R01. However, we will have power to detect large differences between groups as follows. For power calculation, the null hypothesis is that there will be no difference in the FLT bone marrow signal between those allograft patients demonstrating incomplete and complete donor reconstitution on their restaging marrow biopsies, and no difference in the FLT signal within secondary lymphoid tissues between patients with and without acute GVHD.

Complete Donor Reconstitution:

Considering only the 12 allogeneic patients, we will compare the mean FLT bone marrow signal between those with and without complete donor reconstitution. In general we would expect approximately 50-70% of our patients overall to achieve complete donor reconstitution in both the unfractionated and CD3 enriched compartments by transplant day +30.

Assuming equal number of patients with/without Complete Donor Reconstitution:

A sample size of 6 in each group will have 80% power to detect a probability of 0.854 that an observation in the Complete Donor Reconstitution group is less than an observation in the non-Complete Donor Reconstitution group using a Wilcoxon (Mann-Whitney) rank-sum test with a 0.100 one-sided significance level.

Assuming unequal number of patients with/without Complete Donor Reconstitution:

A total sample size of 12 will have 80% power to detect a probability of 0.87 that an observation in the Complete Donor Reconstitution group (n=7) is less than an observation in the non-Complete Donor Reconstitution group (n=5) using a Wilcoxon (Mann-Whitney) rank-sum test with a 0.100 one-sided significance level.

Graft Versus Host Disease:

Considering only the 12 allogeneic patients, we will compare the mean FLT signal within secondary lymphoid tissues in those patients who develop acute GVHD versus those who do not based on the criteria described previously. In general we would expect that approximately 30-40% of our patients will develop some degree of acute GVHD (any site and any clinical grade) by transplant day +100

A sample size of 6 in each group will have 80% power to detect a probability of 0.854 that an observation in the non-GVHD group is less than an observation in the GVHD group using a Wilcoxon (Mann-Whitney) rank-sum test with a 0.100 one-sided significance level.

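### Two-class marrow cellularity, and chimerism used only at the 95% cut, lose information in 12 patients; a supplementary rank correlation would recover it cheaply

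*Combined protocol and SAP*

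**What the plan says.** All references are to the combined protocol and SAP.

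- **Cellularity objectives.** Objective 2.2.5 correlates the day +25 marrow FLT signal "with bone marrow cellularity on transplant day +35 in allogeneic stem cell transplant recipients". Objective 2.2.7 does the same for the day +60 scan and the day +100 biopsy.
- **Cellularity endpoint (2.4.5).** "Bone marrow cellularity will be defined in a dichotomous manner as either hypocellular or normocellular/hypercellular". The source is the pathologist's written report at each of the two restaging biopsies. The documents do not say whether a percentage is reported or abstracted.
- **Chimerism endpoints (2.3.1 and 2.4.1).** "Complete donor reconstitution will be defined as chimerisms" of at least 95% in both the CD3 and the unfractionated compartments. Primary objective 2.1.1 compares marrow signal between recipients "who do and do not go on to achieve complete donor bone marrow reconstitution by transplant day +35".
- **Sample size (8.2).** "Considering only the 12 allogeneic patients, we will compare the mean FLT bone marrow signal" by reconstitution status, with a "rank-sum test with a 0.100 one-sided significance level". About 50 to 70% are expected to reach complete donor reconstitution.
- **Methods (8.3.1).** Wilcoxon rank-sum for group comparisons, and "Spearman and Pearson correlation coefficients will be used to measure correlations between pairs of continuous variables". No item names an analysis of percent chimerism or of graded cellularity. Section 4.5 says only in general terms that imaging will be correlated with chimerism and cellularity.

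**The concern.** Cellularity is a graded property of the marrow, and donor chimerism is a percentage. Once each is cut in two, a patient just below the line counts the same as one far below it, and the rank-sum test sees only group membership. With 12 patients there is little information to spare.

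The correlation methods in 8.3.1 are reserved for continuous pairs, so they do not reach cellularity as 2.4.5 defines it. For chimerism, a 95% rule cannot be applied without a percentage, so the number exists for every patient with a chimerism result, yet no itemised analysis uses it.

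What is at stake is the precision of the preliminary estimates. Section 8.2 says this pilot will be used to power a larger study, and section 4.5 says it seeks quantitative imaging markers of engraftment quality. A graded association serves both aims better than a two-class split alone.

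**Working it through.** **Inputs from the documents.** N = 12 allogeneic patients; one-sided alpha 0.10; rank-sum test; detectable probabilities 0.854 (6 v 6) and 0.87 (7 v 5), each with 80% power; 50 to 70% expected above the chimerism cut.

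**Assumptions, because the documents are silent.** The correlation rho between FLT signal and the graded measure (0.3 to 0.75); bivariate normality; the same 50 to 70% split for cellularity.

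**Step 1. Reproduce the plan's power.** Noether's formula is power = Φ(√(12·c·(1−c)·N)·|p−0.5| − z), with c the fraction in one group and z = 1.282.

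- 6 v 6: √(12 × 0.25 × 12) = 6; 6 × 0.354 − 1.282 = 0.842; power 80.0%.
- 7 v 5: √(12 × 35/144 × 12) = 5.916; 5.916 × 0.37 − 1.282 = 0.907; power 81.8%.

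The stated 80% holds in both cases.

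**Step 2. Cost of cutting.** Each simulated data set draws 12 pairs. Spearman is applied to the uncut measure, and the rank-sum test is applied after cutting it. Power in percent, with 60% / 70% of patients above the cut:

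| rho | Spearman | Rank-sum, exact | Rank-sum, normal approx. | Loss, exact | Loss, approx. |
|---|---|---|---|---|---|
| 0.3 | 35.1 / 35.0 | 25.1 / 23.9 | 30.5 / 30.3 | 10.0 / 11.1 | 4.7 / 4.7 |
| 0.4 | 47.9 / 48.0 | 34.1 / 32.3 | 40.2 / 39.8 | 13.9 / 15.7 | 7.7 / 8.2 |
| 0.5 | 62.3 / 62.4 | 45.3 / 42.3 | 51.9 / 50.6 | 17.0 / 20.2 | 10.3 / 11.8 |
| 0.6 | 76.8 / 76.5 | 58.0 / 54.7 | 64.6 / 63.0 | 18.9 / 21.8 | 12.3 / 13.6 |
| 0.75 | 93.2 / 93.3 | 78.8 / 74.6 | 83.7 / 81.2 | 14.4 / 18.7 | 9.5 / 12.1 |

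An even split costs a little less with the exact test: its power is about 46% at rho 0.5 and 59% at rho 0.6, so the losses are about 62 − 46 = 16 and 77 − 59 = 18 points. The plan's own detectable effect (0.854) corresponds to rho of about 0.75. There the loss over 50 to 70% is 13 to 19 points (exact) or about 8 to 12 (approximation).

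**Step 3. Separate dichotomising from discreteness.** The exact rank-sum test cannot reach 0.10 at these sizes. Its true size is 0.090 at 6/6, 0.074 at 7/5, 0.077 at 8/4 and 0.073 at 9/3, against about 0.10 for Spearman. With the rank-sum test randomised to about 0.10, the loss is 7 to 9 points at rho 0.4, 10 to 13 at 0.5 and 12 to 16 at 0.6.

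**Step 4. Variants.**

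- *A 9/3 split, exact test:* power falls to 37%, 49% and 69% at rho 0.5, 0.6 and 0.75.
- *Chimerism tied at a ceiling (30% of values), rho 0.6:* Spearman drops from 76.8 to 74.9% and the exact-test loss from 18.9 to 17.0 points (60% above the cut). With 50% at the ceiling, Spearman still has 72%.
- *Ordered hypo/normo/hyper only (assumed 40/40/20):* 59% against 52% for two classes at rho 0.5, and 73% against 65% at rho 0.6.

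**The case against.** Several points on the other side stand.

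- **The verb.** A reader might infer that the cellularity correlation cannot be run at all. Objectives 2.2.4 and 2.2.6 use the same verb for transfusion independence, which 2.4.4 makes binary. In this protocol it means association, and the Wilcoxon test in 8.3.1 covers a two-class cellularity endpoint. The plan is analysable as written.
- **The size.** A reader might take a loss of some 14 to 22 points as a property of the trial. It is not. The upper part of the range needs the exact test and middling to high correlations, some of it is discreteness, and 8.3.1 does not say which version of the Wilcoxon test will be used.
- **Data in hand.** For chimerism, the 95% rule implies a recorded percentage. For cellularity, 2.4.5 mentions only a pathology report, so it cannot be said that percent cellularity is collected and then thrown away.
- **Chimerism.** The two-group contrast is the stated primary objective, and its power was planned on that basis. Nothing in 4.5 or 8.3.1 bars a continuous analysis; it is simply not itemised.
- **Multiplicity.** Two compartments at two time points add four correlations in 12 patients.
- **Stakes.** Cellularity is a secondary endpoint with no power claim, in a pilot.

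These points limit the claim to an improvement. They do not remove it: every scenario examined with a real association showed a loss from cutting, and the graded analysis can sit beside the two-class one.

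**Conclusion.** The point holds as a cheap improvement to the analysis plan. Cutting cellularity in two, and using chimerism only at 95%, costs about 4 to 22 points of power relative to Spearman on the graded measure. That range rests on N = 12, one-sided 0.10, bivariate normality, rho of 0.3 to 0.75 and 50 to 70% above the cut. The low end is the normal-approximation test at rho 0.3; the high end is the exact test at rho 0.6 with a 70% split. With test sizes matched, the loss at rho 0.4 to 0.6 is 7 to 16 points. A more lopsided cellularity split would cost more, and the documents give no basis for ruling one out.

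A reader might go further and conclude that the primary comparison or its 80% power is wrong. The documents do not support that: the 95% definition matches objective 2.1.1 and the stated power reproduces.

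**What to change.** 1. **Section 2.4.5.** Abstract percent cellularity where the pathology report gives it. Otherwise abstract the ordered hypo/normo/hyper category, accepting a smaller gain.
2. **Objectives 2.2.5 and 2.2.7, via 8.3.1.** Name Spearman with a confidence interval as the analysis, and keep the two-class comparison as descriptive.
3. **Objectives 2.1.1 and 2.2.1.** Add Spearman of marrow SUV against percent donor CD3 and percent unfractionated chimerism as an exploratory supportive analysis. Leave the 95% definition, the primary test and the stated power unchanged.

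**Cost.** Wording, plus a few numeric fields from at most 12 × 2 = 24 standard-of-care biopsy reports. No new procedures, visits or patients are needed.

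**Downsides to state in the plan.** Percent cellularity is a rough reading and may be missing for some patients. Chimerism values may tie near 100%. The added correlations are exploratory and unadjusted for multiplicity. Their intervals will be wide: by the approximate Fisher transform, an estimate of 0.6 in 12 patients gives 0.693 ± 1.96/√9, that is 0.040 to 1.346, or about 0.04 to 0.87 on the correlation scale.
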